### **9.2.1.3 Time to first PMR flare**

The duration to first PMR flare from clinical remission up to 52 weeks for each group will be analyzed.

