#### **10.4.4 Handling of patients after permanent treatment discontinuation**

Every effort should be made to maintain patients in the study after permanent study treatment discontinuation. Patients should be followed up according to the study procedures as specified in this protocol up to the scheduled date of study completion, or up to recovery or stabilization of any AE to be followed-up as specified in this protocol, whichever comes last. The scientific value of the complete collection of data will be explained to patients, and site personnel will receive training regarding strategies for patient retention, and access to tools to assist with this during the study.

If a patient prematurely and permanently discontinues study treatment, a premature end of treatment (EOT) visit (see [Section 10.4.2](#)) should be scheduled at the time of treatment discontinuation, if possible. If not possible, the EOT should be scheduled as soon as possible after treatment discontinuation. The IRT should be notified of EOT. Of note, during this premature EOT visit, the bone density test does not need to be performed if it has been less than 6 months since the bone density test associated with the baseline visit.

Following the premature EOT visit, the remaining visits will be performed as scheduled. All efforts should be made to follow the patients for safety for at least 6 weeks after last dose of SC IMP and for primary endpoint and key secondary endpoints through the remainder of the study visits up to Week 52 after premature EOT.

All cases of permanent treatment discontinuation should be recorded by the Investigator in the appropriate pages of the CRF when considered as confirmed. Details recording the specific reasons for discontinuation should be collected.

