#### **11.4.2.2 Analyses of secondary efficacy endpoints**

Other binary endpoints (defined in [Section 9.2.1](#)) will be analyzed as described for the primary endpoint (see [Section 11.4.2.1](#)).

The cumulative prednisone (or equivalent) dose will be analyzed using a non-parametric Wilcoxon rank-sum test and the mean and median dose summarized.

Time events will be analyzed by Kaplan-Meier method. Treatment groups will be compared with the use of Cox proportional hazards models. Data censoring will be used for patients who withdraw from the study.

The GTI assessment (total score and domain-specific scores) will be analyzed as other secondary efficacy endpoint using the mixed model repeated measures (MMRM) approach. The model includes treatment, visit, treatment-by-visit interaction as fixed effects, and baseline score as a covariate, will be used to test the difference of the least-square means (LS means) between treatment groups. Descriptive statistics including number of subjects, mean, standard error and LS means will be provided. In addition, difference in LS means, the corresponding 95% CI and the p-value will be provided.

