2.1.3.2 Secondary efficacy endpoint(s)

The following efficacy variables will be assessed:

- Components of sustained remission composite measure at Week 52
- Total cumulative corticosteroid (including prednisone) dose over during the treatment period
- Time to first PMR flare during the treatment period
- GTI Cumulative worsening score (CWS) and Aggregate improvement score (AIS) at Week 52.

Below are descriptions of these variables. Details related to imputation of GTI scores are described in [Section 2.5.2](#).

Components of sustained remission composite measure at Week 52

1. Proportion of patients who achieved disease remission by Week 12.
2. Proportion of patients who have no disease flare from Week 12 through Week 52.
3. Proportion of patients who have normalization of CRP (to <10 mg/L, with an absence of successive elevations to ≥ 10 mg/L) from Week 12 through Week 52.
4. Proportion of patients who successfully adhere to the prednisone taper from Week 12 through Week 52.

Total cumulative corticosteroid (including prednisone) dose during the treatment period

The total cumulative corticosteroid includes prednisone taper regimen per protocol, add-on prednisone prior to Week 12 or use of commercial prednisone during the study treatment period such as those employed to manage AE not related to PMR, and rescue corticosteroids dose prescribed for rescue therapy over the treatment period for PMR disease only.

Time to first PMR flare during the treatment period

The duration (in days) from randomization to first PMR flare after clinical remission and up to 52 weeks. Patients who never achieve remission will be censored at randomization day; and those who achieved clinical remission and never flared will be censored at the end of treatment assessment date up to Week 52.

The definition of PMR flare is provide in [Section 2.1.3.1](#) primary efficacy endpoint.

Clinical remission is defined as resolution of signs and symptoms and normalization of CRP (<10 mg/L). Intermittent missing CRP at visit will be imputed using last value carried forward (LOCF) approach. If missing signs and symptoms, then clinical remission is not achieved.

Glucocorticoid toxicity index (GTI) scores and components

The GTI is intended to capture glucocorticoid (GC)-related morbidity and GC-sparing ability of other therapies (2).

The GTI is composed of two components, the Composite GTI and the Specific List ([Table 2](#)).

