2.4.4.2 Analyses of secondary efficacy endpoint(s)

Components of sustained remission composite measure at Week 52

Descriptive statistics (i.e., counts and percentages) will be provided for the following binary variables by treatment groups:

- Patients who achieve disease remission by Week 12
- Patients who have absence of disease flare from Week 12 through Week 52
- Patients who have normalization of CRP (decrease to <10 mg/L) with sustained normalization from Week 12 through Week 52
- Patients who successfully adhere to the prednisone taper from Week 12 through Week 52

Total cumulative corticosteroid (including prednisone) dose

Descriptive statistics including the number of subjects, mean, and median of the total cumulative prednisone (or equivalent) dose will be presented for each treatment group. The difference between the medians and the corresponding 95% non-parametric confidence interval along with p-value from the non-parametric Wilcoxon rank-sum test between the treatment groups will also be provided.

Both expected and actual cumulative CS dose will be presented. The expected cumulative dose is based on CS tapering regimen up to end of treatment, assuming that the taper was continued without error while actual cumulative CS dose will be calculated as the total cumulative CS used for PMR disease up to the end of treatment, including expected prednisone in tapering regimen per protocol, add-on prednisone, CS used in rescue therapy and the use of commercial prednisone. Patients who received increased prednisone or equivalent in rescue therapy will be included in their original treatment groups.

In the scenario that a patient has already taken external CS for the disease before randomization on the day of randomization, the CS dose taken will be considered as the first dose of oral IMP. The first dose of prednisone per tapering regimen will be skipped, and the patient will take the second dose of prednisone on the next day.

Time to first PMR flare during the treatment period

Time (from randomization) to the first PMR flare after clinical remission up to Week 52 will be analyzed by Kaplan-Meier method providing the median, 25th and 75th percentiles (where possible) along with the 95% CI for the median. The comparison between the treatment groups will be performed using Cox proportional hazards model. Hazard ratio and the corresponding 95% CI and p-value will be provided.

Composite GTI and Specific List

GTI analyses

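### SAP 2.1.3.2 counts first flares up to Week 52 but censors flare-free patients at the end-of-treatment visit, so the two windows differ for patients who stop drug early and stay in the study

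*SAP*

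**What the plan says.** SAP 2.1.3.2 defines the endpoint as "The duration (in days) from randomization to first PMR flare after clinical remission and up to 52 weeks". SAP 2.4.4.2 keeps that window: "Time (from randomization) to the first PMR flare after clinical remission up to Week 52 will be analyzed by Kaplan-Meier method", with a Cox hazard ratio, 95% CI and p-value. On censoring, SAP 2.1.3.2 says "those who achieved clinical remission and never flared will be censored at the end of treatment assessment date up to Week 52". In both sections the heading confines the endpoint to the treatment period. No sentence says whether a flare after a premature end-of-treatment (EOT) visit counts. SAP 2.4.4 assigns the secondary efficacy endpoints to the ITT population.

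Protocol 9.2.1.3 reads: "The duration to first PMR flare from clinical remission up to 52 weeks for each group will be analyzed". Protocol 11.4.2.2 adds: "Data censoring will be used for patients who withdraw from the study", without naming a date. Under Protocol 10.4.4 the premature EOT visit "should be scheduled at the time of treatment discontinuation, if possible". The same section then says: "Following the premature EOT visit, the remaining visits will be performed as scheduled", and asks for follow-up "for primary endpoint and key secondary endpoints through the remainder of the study visits up to Week 52 after premature EOT".

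**The concern.** For a patient who completes treatment, the EOT visit is the Week 52 visit and the two windows coincide. For one who leaves drug and study together they nearly coincide. They separate for a patient in remission who stops drug early, has not flared, and keeps attending visits.

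Take such a patient with an EOT visit at Week 20. If a flare follows at Week 32, the literal text puts the patient in the risk set to Week 32 with an event. If no flare follows, the patient leaves the risk set at Week 20. Time at risk after Week 20 is therefore kept only for early stoppers who go on to flare. The censoring time depends on the later outcome, and the estimated hazard rises in whichever arm has more early stopping.

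The other way to read the text is that the heading governs and flares after EOT are not counted. That is coherent, but it is an on-treatment analysis that the SAP does not label as one, and it sets aside data that Protocol 10.4.4 plans to collect. Either way, the programmer is left to choose the analysis.

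**Working it through.** **No figure to reproduce.** The documents give no event count, hazard ratio (HR) or power for this endpoint. The primary power table for 59 per group does reproduce (25-point difference: 95.6%, 91.2% and 87.0%, against 95.6%, 91.2% and 86.9% stated), but it has no bearing here. Flare risks, stopping rates and hazards after stopping are not in the documents; all values below are assumptions.

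**Rules compared.** T is the flare time and D the stopping time, in weeks, with c = min(D, 52).
- One window to Week 52: time min(T, 52), event if T ≤ 52.
- Both ending at EOT: time min(T, c), event if T ≤ c.
- Literal SAP text: event at T if T ≤ 52, otherwise censored at c.

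Times are exponential, with weekly flare hazard −ln(1 − p)/52 for a 52-week risk p; all patients are in remission from the start. Stopping rates are given as sarilumab / placebo.

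**Illustration 1.** 52-week flare risk 30% sarilumab and 60% placebo; 20,000 patients per arm. True on-drug HR = ln(0.70)/ln(0.40) = 0.389.

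| Stopping | Sarilumab hazard after stopping | One window | Both end at EOT | Literal |
|---|---|---|---|---|
| 25% / 10% | unchanged | 0.397 | 0.400 | 0.432 |
| 25% / 10% | doubled | 0.427 | 0.387 | 0.451 |
| 25% / 10% | fourfold | 0.502 | 0.399 | 0.514 |
| 10% / 25% | unchanged | 0.378 | 0.379 | 0.359 |

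**Illustration 2.** 50% flare risk on placebo; off-drug hazard equal to the placebo hazard; 200,000 patients per arm.

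| True on-drug HR | Stopping | One window | Both end at EOT | Literal |
|---|---|---|---|---|
| 1.00 | 20% / 20% | 1.004 | 1.004 | 1.004 |
| 1.00 | 30% / 10% | 0.998 | 0.997 | 1.086 |
| 1.00 | 10% / 30% | 0.996 | 0.997 | 0.915 |
| 0.50 | 20% / 20% | 0.548 | 0.505 | 0.543 |
| 0.50 | 30% / 10% | 0.569 | 0.502 | 0.615 |

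The literal rule moves against the arm with more stopping in both directions. With equal stopping it does not move under no effect, and hardly moves otherwise (0.548 to 0.543).

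**Type I error** (59 per arm, 4,000 trials, no true effect, simulation error about 0.4 points). The literal rule gives 4.7% at 20% / 20%, 6.2% at 30% / 10% and 7.7% at 40% / 10%. The single window gives 5.2%, 4.5% and 5.0% in the same trials.

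**Flares lost if both end at EOT**, per 118 patients with true on-drug HR 0.50: 48.8 − 42.8 = 6.0 at 30% / 10%, and 48.7 − 39.8 = 8.9 at 30% / 30%.

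**Scale against noise**, using the Illustration 1 risks: expected flares are 59 × 0.60 = 35.4 and 59 × 0.30 = 17.7, so SE(log HR) is about √(1/35.4 + 1/17.7) = 0.29. The literal shift is ln(0.432/0.397) = 0.085, about 0.3 of a standard error.

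**The case against.** The strongest reply is that the heading settles the matter: the endpoint concerns the treatment period and Week 52 is only the outer cap. Ending both events and censoring at EOT is then legitimate. This largely stands. A reader might infer that such censoring is informative and biases the hazard ratio. The figures do not show that: with both ending at EOT, the results of 0.400, 0.387 and 0.399 recover the on-drug value of 0.389 whatever happens after stopping. The gaps from the single-window results (0.43 and 0.50) are differences between two estimands. Informative censoring would require stoppers to differ in on-drug risk, which these models do not include. What remains is that the SAP neither labels the analysis as on-treatment nor excludes later flares.

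A reader might also infer an undeclared change from the protocol. Protocol 11.4.2.2 names patients who leave the study but gives no date and does not say that only they are censored. The statement in SAP 1.6 that the efficacy plan is unchanged is about the early end of recruitment. The fair statement is a departure from the natural reading of the protocol.

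Nor do the documents support saying that the rule flatters sarilumab. Read literally, it penalises whichever arm stops more, and the rates are not given. SAP 2.1.3.1 already counts patients who permanently stop treatment as failures on the flare component of the primary endpoint.

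It can be argued that flare has no meaning once a patient is off the blinded taper, since a dose increase is defined relative to that taper. This does not hold: SAP 2.1.3.1 identifies flares in practice from the reason recorded for rescue steroid on the eCRF, and SAP 2.1.2 has all corticosteroids during the study reported.

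Two points stand in full. Visits after discontinuation are planned but cannot be assured, and the effect is modest and rests on assumptions.

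**Conclusion.** The mismatch between the event window and the censoring date is real and should be resolved. Taken literally, the rule makes censoring depend on the later outcome, and no estimand justifies that. Under the stated assumptions the hazard ratio shifts from about 0.40 to 0.43 at 25% / 10% stopping, and reads 1.09 (or 0.92 with stopping reversed) under no effect at 30% / 10%. There is no shift under no effect if stopping is equal. If the text is meant to exclude flares after EOT, the fault is an unlabelled on-treatment analysis that fits poorly with the ITT statement and the planned follow-up; bias is not demonstrated.

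The size depends on how many patients stop drug and stay in the study, which the documents do not give. Time to first flare is outside the testing sequence, where SAP 2.4.4.4 places only cumulative corticosteroid dose after the primary endpoint. The primary conclusion is not touched.

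**What to change.** State one window for events and censoring in SAP 2.1.3.2 and 2.4.4.2. Count first flares after remission up to Week 52 whether or not treatment was discontinued, identified by the eCRF rescue-therapy reason already used in SAP 2.1.3.1. Censor remitted, flare-free patients at Week 52, or at their last PMR assessment before study withdrawal if earlier. Remove the treatment-period limit from the heading of this analysis. Keep an on-treatment version, with both events and censoring ending at EOT, as a labelled supportive analysis. Report by arm how many patients stopped drug and remained in follow-up.

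If the sponsor prefers the on-treatment version as the main one, the SAP should say so, exclude flares after EOT explicitly and give the reason in SAP 1.6. The choice should be fixed before unblinding.

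The cost is a few sentences and a changed censoring date in the program. Planned visits and steroid records already supply the data, although follow-up after discontinuation may be incomplete for some patients.

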#### Signs and symptoms of PMR

Evaluation for clinical signs and symptoms by the Efficacy Assessor at every study visit according to the schedule of assessment should include, but are not limited to, the following:

- Morning stiffness and/or pain, in the neck, shoulder and/or hip girdles
- Limited range of motion of the shoulders and/or hip girdles
- Constitutional symptoms, such as fatigue, weight loss and low-grade fever
- Other features judged by the clinician-investigator to be consistent with a PMR flare

**Flare** is defined as either 1) recurrence of signs and symptoms attributable to active PMR plus an increase in CS dose due to PMR, or 2) elevation of ESR attributable to active PMR plus an increase in CS dose due to PMR.

Increase in CS dose is defined as:

- Any dose increase during the protocol-defined steroid taper
- Re-initiation of prednisone therapy after the protocol defined taper has been completed

*Note: During the initial 12 weeks of prednisone taper, treatment for one flare before Week 12 is permitted if it can be successfully treated with a low dose ( $\leq 5$  mg/day) prednisone add-on taper regimen (completed prior to Week 12) and provided that all other sustained remission parameters are met.*

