## Appendix C COMPOSITE Glucocorticoid Toxicity Index

1. Body Mass Index (BMI) (compared to baseline)
 

a. Improvement in the direction of the normal range by more than 2 BMI units [normal range = 18.5-24.9 kg/m^2]

b. No significant change (BMI remains within +/- 2 BMI units compared with baseline) OR BMI remains within the normal range

c. Moderate increase in BMI (increase by more than 2 but less than 5 BMI units, to above the upper limit of normal BMI [24.9 kg/m^2])

d. Major increase in BMI (increase by at least 5 but less than 8 BMI units above normal BMI [24.9 kg/m^2])

2. Glucose Tolerance (compared to baseline)
 

a. Improvement in glucose tolerance:

• HbA1c declined >10% from baseline without medication increase OR

• Decrease in diabetic medication without an increase in HbA1c of >10% or HbA1c < 5.7%

b. No significant change in glucose tolerance:

• HbA1c within 10% of baseline or HbA1c < 5.7% AND no change in medication OR

• HbA1c increased to > 10% of baseline with a decrease in medication OR

• HbA1c decreased by > 10% of baseline with an increase in medication

c. Worsening of glucose tolerance or medication status:

• HbA1c > 5.7% and increased to >10% of baseline without a change in medication OR

• Increase in diabetic medication with < 10% increase in HbA1c

d. Worsening of glucose tolerance despite increased treatment:

• HbA1c > 5.7% AND increased to >10% of baseline AND an increase in diabetic medication

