1.6 STATISTICAL MODIFICATIONS MADE IN THE STATISTICAL ANALYSIS PLAN

Due to the premature termination of the study, a total of 118 patients (42%) of the 280 patients planned were randomized. The randomized patients could continue in the study to complete the treatment period and the 6 weeks post-treatment follow up per protocol. Hence, there are no changes to the efficacy analysis plan per protocol.

The COVID-19 pandemic has also impacted data collection as patients may not be able to visit clinical sites for endpoint assessments. Additional patient level information at visits that were impacted by the pandemic situations were captured for assessments performed in visits that were delayed, not done, partially done on site, or partially done by phone. Major or critical COVID-19 impacted deviations per protocol were also recorded.

To assess the impact of the pandemic on the study, COVID-19 related summaries are added as below.

- a) Patients who permanently discontinue study treatment or study due to COVID-19 reasons will be summarized in patient disposition table
- b) Patient disposition by visit according to trial impact due to COVID-19
- c) Critical or major deviations summary according to COVID-19 impact
- d) Number (%) of patients experiencing at least one treatment-emergent COVID-19 related adverse event by primary SOC and PT

In addition, if > 10% patients are impacted by the COVID-19 pandemic, below summaries/analyses will be generated by COVID-19 impacted population (Yes, No):

- a) Extent of exposure to SC IMP
- b) Treatment compliance for SC IMP

- c) Number (%) of patients with TEAEs by primary SOC and PT, and
- d) Analysis of the primary endpoint of sustained remission at Week 52.

The population with and without trial impact (disruption) due to COVID-19 is defined in [Section 2.3.4](#).

In addition, upon meeting with Japan Health Authorities (PMDA) in April 2019, data for the components to calculate the PMR activity score (PMR-AS) were subsequently collected and the analysis plan is described in [Section 2.4.4.3](#).

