The Composite GTI consists of nine domains (body mass index (BMI), glucose tolerance, blood pressure, Hyperlipidemia, Bone Health (BMD), steroid myopathy, Skin steroid-related Toxicity, Neuropsychiatric – steroid related symptoms and infection) on common steroid-related adverse events anticipated to occur in $\geq 5\%$ of patients treated in a clinical trial involving glucocorticoids. The Specific List consists of 23 items (11 domains) that are mainly less common but serious adverse effects, serving as a complementary tool to the Composite GTI to ensure that all important elements of glucocorticoid toxicity were captured.

The domains of the Composite GTI and the specific list of the GTI will be assessed at baseline, Week 12, Week 24, Week 40 and Week 52, except for bone density (BMD) which will be assessed at Baseline and Week 52 only.

For patients who withdraw from the study prior to Week 24, BMD will not be measured at the EOT visit as no substantial changes are expected within 6 months of treatment. As a result, missing BMD score will be imputed as 'no change'. The BMD measured at the end of treatment (EOT) visit will be included in the definition of cumulative GTI scores (i.e., CWS and AIS as defined below) at Week 52 regardless when the EOT visit occurred.

Scoring of the Glucocorticoid Toxicity Index (GTI)

Domain-specific score for each patient at a visit is defined as the weight assigned based on the change in severity level as described for each domain in [Table 2](#).

Composite GTI score for each patient at a visit is the sum of 9 domain-specific scores at each visit.

Cumulative GTI score is the sum of composite GTI score across visits. Two cumulative GTI scores, CWS and AIS, will be defined.

- **Cumulative worsening score (CWS)**

CWS is designed to assess cumulative GC toxicity, regardless of whether the toxicity has lasting effects or is transient. New toxicities that occur are added, but toxicities that appear to resolve on follow-up are not removed. Thus, the CWS serves as a lasting record of GC toxicity observed and can only increase or remain the same over time.

CWS will be lower in the treatment arm compared to the placebo arm at the end of trial, if the treatment is effective at decreasing GC toxicity over time.

- **Aggregate improvement score (AIS)**

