- b) For improvement score, only the most severe infection occurring over the course of the entire trial is scored.

Step 2: Calculate composite worsening score and improvement score at each visit by summing the 9 domain-specific score.

- a) For composite worsening score, sum the 9 domain-specific worsening scores.
- b) For composite improvement score, sum the 9 domain-specific improvement scores.

Step 3: Calculate cumulative GTI scores by summing composite scores across visits.

- a) For CWS at Week 52, summing composite GTI worsening score at Week 12, Week 24, Week 40, and Week 52.
- b) For AIS at Week 52, summing composite GTI improvement score at Week 12, Week 24, Week 40, and Week 52.

Table 2 – The Glucocorticoid Toxicity Index

Composite GTI	Item weight	Specific List¹
1.BMI		
Decrease by \geq 5 BMI units	-36	Major increase in BMI
Decrease by >2 but <5 BMI units	-21	
No significant change (\pm 2 BMI units)	0	
Increase of >2 to <5 BMI units	21	
Increase of 5 or more BMI units	36	

Composite GTI	Item weight	Specific List¹
2.Glucose tolerance		
Improvement in HbA1c AND decrease in medication	-44	Diabetic retinopathy
Improvement in HbA1c OR decrease in medication	-32	Diabetic nephropathy
No significant change	0	Diabetic neuropathy
Increase in HbA1c OR increase in medication	32	
Increase in HbA1c AND increase in medication	44	
3.Blood pressure		
Improvement in BP AND decrease in medication	-44	Hypertensive emergency
Improvement in BP OR decrease in medication	-19	Posterior reversible encephalopathy syndrome
No significant change	0	
Increase in BP OR increase in medication	19	
Increase in BP AND increase in medication	44	
4.Hyperlipidemia		
Decrease in LDL AND decrease in medication	-30	
Decrease in LDL OR decrease in medication	-10	
No significant change	0	
Increase in LDL OR increase in medication	10	
Increase in LDL AND increase in medication	30	
5.Bone Health (BMD)		
Increase in BMD (gain of more than 3%)	-29	Major decrease in bone density
No significant change in BMD (+/- 3%)	0	Insufficiency fracture
Decrease in BMD (loss of more than 3%)	29	
6.Steroid myopathy		
Moderate weakness to none	-63	Severe steroid myopathy
Moderate to Mild weakness	-54	
Mild weakness to none	-9	
No significant change	0	
None to Mild weakness (without functional limitation)	9	
Mild to Moderate weakness	54	
None to Moderate weakness (with functional limitation)	63	
7.Skin steroid-related Toxicity		
Decrease in Skin Toxicity – Moderate to None	-26	Severe skin toxicity

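### SAP Table 2 scores BMI on raw change alone and drops protocol Appendix C's normal-range conditions without listing the change, so weight change within the normal range moves AIS and CWS

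*SAP*

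**What the plan says.** **Protocol Appendix C, item 1 (BMI).** Change is measured from baseline, in four categories, with 18.5-24.9 kg/m² as the normal range:

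- Improvement: "Improvement in the direction of the normal range by more than 2 BMI units".
- No significant change: within 2 units of baseline, "OR BMI remains within the normal range".
- Moderate increase: "increase by more than 2 but less than 5 BMI units, to above the upper limit of normal BMI" (24.9).
- Major increase: at least 5 units, again set against 24.9.

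Appendix C gives no numeric weights.

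**SAP 2.1.3.2.** The domain score "is defined as the weight assigned based on the change in severity level as described for each domain in" Table 2. Table 2 has five BMI bands: -36 for a fall of 5 or more units, -21 for "Decrease by >2 but <5 BMI units", 0 within 2 units either way, +21 for a rise of more than 2 but less than 5, and +36 for a rise of 5 or more. No band mentions the normal range, and the table names no reference visit.

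For the worsening score, negative domain scores are set to 0. For the improvement score they are kept. CWS and AIS at Week 52 are sums over Weeks 12, 24, 40 and 52. The SAP reads a negative AIS as toxicity that has resolved.

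**SAP 2.4.4.2.** CWS and AIS are compared by ANCOVA. Patients are also split at CWS = 0 versus above 0, and at AIS below 0 versus 0 or more.

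The Table 2 footnote, SAP 2.5.2 and SAP Appendix J do not bring the normal-range conditions back. SAP 1.5 and 1.6 do not list their removal.

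**The concern.** The two documents give different scores for the same patient, and the SAP rule is the one that will be programmed. A patient with a normal BMI throughout has no BMI toxicity in the protocol's sense. Table 2 can still credit that patient with resolved toxicity or charge new toxicity.

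Weight change in this disease is not only a steroid effect. Protocol 9.1.1 lists "Constitutional symptoms, such as fatigue, weight loss and low-grade fever" among the signs of PMR, and SAP 2.1.1 lists unintentional weight loss as a baseline symptom. Loss from active disease in a normal-weight patient can therefore lower AIS. Regain of weight lost before baseline can raise both AIS and CWS. CWS and AIS are the SAP's only GTI secondary endpoints and are meant to show a steroid-sparing benefit, so points from this source blur what the comparison means.

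**Working it through.** **Inputs.** BMI rules from protocol Appendix C; BMI bands from SAP Table 2; four scored visits from SAP 2.1.3.2; stated score range from protocol 9.2.1.4.

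**The one GTI figure the plan states.** Protocol 9.2.1.4 gives a range of -36 to 439. The largest Table 2 weights sum to 36+44+44+30+29+63+26+74+93 = 439, which agrees. The most negative weights sum to -(36+44+44+30+29+63+26+74) = -346, which does not. This mismatch comes from eight domains, not from BMI alone, and is a separate matter.

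**The two BMI rules on the same patients.**

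| BMI change | SAP Table 2 | Protocol Appendix C |
|---|---|---|
| 24.0 to 21.5 | -21 | no change |
| 24.8 to 19.5 | -36 | no change |
| 21.5 to 24.0 | +21 | no change |
| 19.5 to 24.8 | +36 | no change |
| 17.5 to 20.0 | +21 | improvement |
| 20.0 to 17.5 | -21 | no category applies |
| 26.0 to 23.0 | -21 | improvement |
| 23.0 to 26.0 | +21 | moderate increase |

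The last two rows agree in direction. The first four differ, the fifth reverses direction, and in the sixth a fall into underweight is credited as improvement.

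**Contribution at Week 52 (sum of four visits).** The result depends on the reference visit, which Table 2 does not name.

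| BMI path (baseline, then Weeks 12, 24, 40, 52) | Against baseline | Against prior visit |
|---|---|---|
| 24.0, then 21.5 throughout | AIS -84, CWS 0 | AIS -21, CWS 0 |
| 21.5, then 24.0 throughout | AIS +84, CWS +84 | AIS +21, CWS +21 |
| 24.0, 21.5, 21.5, 24.0, 24.0 | AIS -42, CWS 0 | AIS 0, CWS +21 |

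For a lasting change, 21 × 4 = 84 and 36 × 4 = 144 are upper limits that require scoring against baseline at all four visits. Against the prior visit the change scores once, 21 or 36. Under Appendix C all three paths score 0.

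**How large a weight change is needed.** At an assumed height of 1.65 m, 2 units is 2 × 1.65² = 5.4 kg (4.8 kg at 1.55 m, 6.1 kg at 1.75 m). The normal range is 24.9 - 18.5 = 6.4 units wide, so a 36-point change inside it is possible but needs at least 5 × 1.65² = 13.6 kg.

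**Classification.** With the other domains at zero, a lasting loss inside the range makes AIS negative (improved) and a lasting gain makes CWS positive (worsening), under either reference visit.

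**Consistency within the SAP.** Appendix J gives 0 baseline BMI points below BMI 27. A patient at 24.0 who falls to 21.5 is then credited with resolving a toxicity that the SAP itself scored as absent.

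**The case against.** **Table 2 may be shorthand.** It also omits Appendix C's 10% and target conditions for HbA1c, blood pressure and LDL, and SAP 2.5.2 says that measurements are combined with a GTI case report form, which is not supplied. This stands for those domains. It does not rescue BMI, whose rows carry a complete numeric rule that can be programmed as it reads. If the form applies Appendix C, the SAP needs to say so.

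**The SAP may use another GTI version.** It has symmetric negative weights, CWS and AIS, and a baseline BMI threshold of 27, none of which is in Appendix C. The documents therefore show an undeclared divergence. They do not show that raw BMI bands are wrong for whatever version was meant. That part stands, and it is why declaring and justifying the departure is an acceptable remedy.

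**Stronger readings that the documents do not support.**

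- That weight loss makes an arm look less toxic on both scores. Negative BMI scores become 0 in the worsening score, so loss earns credit only in AIS.
- That any regain counts as toxicity. Regain of weight lost before baseline can, under either reference visit. Regain of weight lost during the trial does so only against the prior visit.
- That 84 or 144 points is the usual effect. Those totals need change from baseline, while the SAP's wording on adding new toxicities and on scoring intervals fits visit-to-visit change better.
- That SAP 1.6 misdescribes the GTI scoring. "Hence, there are no changes to the efficacy analysis plan per protocol" follows from patients completing the study after early termination. The narrower fact is that neither 1.5 nor 1.6 lists the change.
- That Appendix C would remove the mixing with disease activity. An overweight patient who loses weight from active PMR is improved there too.

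**Conclusion.** The concern holds as an undeclared departure from the protocol with a definite direction at patient level. Each affected patient is misscored, relative to Appendix C, by 21 or 36 points per scored visit: once for a lasting change if the reference is the prior visit, up to 84 or 144 in total if it is baseline. For an underweight patient moving toward normal, the sign is reversed.

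The effect on the treatment comparison cannot be sized. The documents do not say how many of the 118 patients have a normal or low BMI and change by more than 2 units, or how they divide between arms, so no direction of bias between arms can be asserted.

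CWS and AIS lie outside the testing sequence in SAP 2.4.4.4. The primary test and the cumulative corticosteroid dose test are unaffected. The point should be corrected because the GTI results will be read as evidence of steroid sparing, but it does not threaten the trial's main conclusion.

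**What to change.** In SAP Table 2, restore the Appendix C conditions for BMI, keeping the table's weights by size of change:

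- 0 if the change is within 2 units, or if BMI is within 18.5-24.9 at both baseline and the visit.
- A negative weight only for a change of more than 2 units toward the normal range, from above or from below.
- A positive weight only for an increase of more than 2 units that ends above 24.9.
- 0, not improvement, for a fall below 18.5 or further below it, since Appendix C has no category for this.

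State the reference visit. Appendix C says baseline; with four visits summed, a lasting change then counts four times, and the SAP should say whether that is intended.

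If a different GTI version is meant, name it in SAP 1.6 and justify dropping the normal-range conditions. Reconcile the score range in protocol 9.2.1.4 with Table 2 as a separate correction.

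The cost is table wording and derivation code. Height is recorded at screening, and weight at baseline and Weeks 12, 24, 40 and 52, so no new data are needed.
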